# 1.2 Describe any relevant preliminary data.

In the completed first phase of this project, we made a variety of discoveries.

In Aims 1 & 2 [*Please see IRB ID 2020-0749 & 2019-0058*] we examined individual-, area-, and system-level factors that may influence access to care following release from prison. The study cohort for Aim 1 included adults living with, or at risk of, SUD, HCV, or HIV who were enrolled in Medicaid at the time of their release from Wisconsin state prison. Preliminary results indicated that within 30-days of their release, approximately 34% of the study population has at least one outpatient visit. Women are more likely than men to have this visit as are White individuals compared to Black individuals. Receipt of prescription medication indicated for the following conditions during the 12-months before release from prison strongly increase the likelihood of an outpatient visit within 30-days: HIV, depression, diabetes, pain, Parkinson's disease, psychotic illness, osteoporosis/Paget's, and alcohol dependence. Aim 2 examined the impact of assistance with Medicaid enrollment pre-release on access to care among those with and without a history of SUD. For those with a history of SUD, we find significant increases in the likelihood of outpatient care for any cause and related to substance use disorders. However, the absolute rate of SUD-related care remains low.

AIM 3: Qualitative research done from 2019-2021 contributed directly to how the C-TraC intervention was modified to fit the present study's target population. Firstly, general challenges (e.g. access to transportation, access to cell phones) were identified by both the focus group participants as well as the interview participants. This information allowed us to consider the scope of the Nurse Case Manager's intervention and how these needs could be met while controlling the scale of the intervention to a feasible level.

Interviews conducted with formerly incarcerated adults also yielded valuable information concerning the importance of rapport and trust building with people who are incarcerated. Based on interviews with formerly incarcerated individuals, strategies have been added to the Nurse Case Manager protocol to individualize case management to prevent participants from feeling like the Nurse Case Manager is using a checklist or "just doing a job".

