# State the hypotheses to be tested.

The main hypothesis to be tested in this pilot study is that the CJC-TraC protocol developed in collaboration with WIDOC partners will be successfully implemented in a way that is deemed acceptable to WIDOC staff and incarcerated patients. We will consider implementation to be successful if (1) we enroll a substantial number of eligible participants (e.g. at least 50% of the targeted sample size of 220), and (2) Participants complete post-incarceration study activities with a reasonable rate of retention (e.g. fewer than 50% of participants being lost to follow-up after

release). We will assess acceptability by systematically querying study participants and WIDOC staff about their experience with CJC-TraC using validated questionnaires, as described below.

A secondary hypothesis is that individuals who participate in the CJC-TraC pilot will have a higher rate of using non-emergency, outpatient health services (e.g. primary care clinic appointment) after incarceration, in comparison to contemporaneous rates of health service utilization by individuals with comparable levels of comorbidities and demographic characteristics.

2.2 Define the primary and secondary study endpoints. A study endpoint is a specific measurement or observation to assess the effect of the study variable (study intervention). Study endpoints should be prioritized and should correspond to the study objectives and hypotheses being tested.

In this pilot study we will assess endpoints related to feasibility, acceptability, and effectiveness, as described above:

Primary Endpoints: Feasibility

- The number of participants who are enrolled and complete the baseline study assessment per month, at each of two institutions;
- The number of pre-release CJC-TraC intervention sessions completed with the nurse case manager for each participant, at each institution;
- The number of post-release telephone contacts between the CJC-TraC nurse case manager and study participants;
- The proportion of study participants who are retained in follow-up for three months and complete the end-of-study assessment.

Primary Endpoints: Acceptability

- The proportion of study participants who rated specific aspects of the intervention useful and encounter volumes appropriate, collected on 3 month survey.
- The subjective experience in the program regarding prison-to-community transition support and healthcare support, collected by participant interview.

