# 13.4 What data will be collected during the study and how that data will be obtained.

• List of data elements

**Primary Objective:** The following data elements will be collected from the EMR/Department of Corrections documents or databases. The data will be manually extracted on-site by the Nurse Case Manager or Research Assistant for the purpose of assessing eligibility (pre-consent), and formulating a re-entry plan (post-consent).

- Name (first, middle initial, last)
- Date of Birth
- Race/ethnicity
- Sex
- Insurance status at release
- Medical history
  - o Medications
  - Diagnoses/problem list
  - Procedures or previous treatments

Page 24 of 37

- Dates and test results for HIV and HCV
- o Previous and upcoming medical appointments
- Post-release health care use

The following data elements will be collected from the participant:

- Social Determinates of Health plan post-release
  - Housing
  - Employment
  - Transportation
  - Health Literacy Screening and history
- Family engagement plan or other sources of support post-release
- Lifetime years spent in:
  - o Prison
  - o Jail
- Number of times incarcerated in lifetime
- Amount of time spent incarcerated during current incarceration
- Pre-incarceration:
  - History of drug/substance misuse prior to incarceration
  - Use of primary care services prior to incarceration
  - o Health insurance coverage prior to incarceration
- Pre-incarceration social determinants of health
  - Homelessness/housing insecurity

**Secondary Objective:** Please see **Appendix 2** for all data elements and their sources for the secondary objective.

- Post-release health care use
  - Questionnaires, structured interviews, or other assessments. (Upload all surveys, scripts, and data collection forms in the ARROW application.)

(Please see Appendix numbers 1, 3, 4 for more details on this information)

For data collection, participants will be asked to complete the questionnaire in the Encounter Guide.

 
Sc
 
	ource records that will be used to collect data about participants. Check all
so	urces that apply:
	Services
	□ Data from publicly available datasets (e.g., U.S. census data)
	X□Data from outside institutions or organizations (specify: Wisconsin Medicaid Data,
COMF	PAS Case Management and Risk Assessment Instrument, DOC Central Pharmacy
Datab	ase, Wisconsin Electronic Disease Surveillance System DOC Administrative Records
	□ Other (specify: )

Revised: February 16, 2023

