The proposed sample size was chosen by considering what would be an appropriate case load and frequency of client interactions for the Nurse Case Manager. This level was informed by focus group data collected in Phase 1 and input from collaborators, and eligible participants at the two correctional institutions where the study will occur. Publicly available data from the Department of Corrections indicates that Oakhill Correctional has approximately 316 annual releases while Robert E. Ellsworth Correctional Center (REECC), a facility in the Wisconsin Women's Correctional System (WWCS), has approximately 327, for a total of 643 annual releases at the two study sites. There are 112 and 65 people released to Dane and Milwaukee counties annually at Oakhill and REECC respectively, for a total of 177. These counties will be prioritized for recruitment. An additional 126 individuals released annually to Rock, Waukesha, Racine, and Kenosha counties, 62 from Oakhill and 64 from REECC. These counties can be adequately serviced by the NCM at this time, and the number of serviceable counties will increase throughout the intervention. Assuming that 50% of people incarcerated at the two facilities and releasing to a serviceable county will be eligible and enroll in the study, we would expect a total of 168 participants at Oakhill Correctional Institution and 120 at REECC over the 24-month study period, for a total of 288 total participants. Our recruitment goal is 220 individuals.

20.3 Participant Population(s) for Analysis: Identify and describe the analysis datasets (e.g., which participants/populations will be included in each).

The dataset construction begins with all individuals released from a WI state correctional facility between 1/2020-12/2023. From this universe of individuals, we will apply the sample criteria noted in 5.4 to generate the analytic dataset: adults who have a history of, or living with, SUD, HCV or HIV and enroll in Medicaid within the month of release.

20.4 Statistical Methods: Summarize the overall statistical approach to the analysis of the study data.

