We will implement descriptive analyses to achieve the following objectives: a) to characterize and compare the equivalence of sample characteristics and outcomes across study years; b) to describe, and test for change over time in unadjusted study outcomes; and c) to quantify the association between study outcomes and factors that may influence those outcomes including beneficiary characteristics. We will use bivariate statistical tests (e.g., t-test, chi-square test) to determine the equivalence of unadjusted characteristics and outcomes over time, and regression methods to estimate changes over time in study outcomes, controlling for individual and areas-level characteristics. For binary outcomes, we will implement logistic regression. For count outcomes, we will implement Poisson regression.

20.5 Planned Interim Analysis: Interim efficacy or safety analyses if planned, and include a description for stopping rules for efficacy and stopping rules for safety.

Interim analyses for feasibility and fidelity will be conducted aligned with the Replicating Effective Programs, such as logging the intensity and frequency of time spent by the Nurse Case Manager on participants, as well as analyses to identify statistically significant barriers to accessing care after release.

20.6 Handling of Missing Data: Describe how missing data will be handled, e.g., type of imputation technique, if any, and provide justification. (Most methods for handling missing data assume that the data are missing at random, which may not be a valid assumption.) WIDOCument reasons for missing data and evaluate the impact of missing data using sensitivity analysis. (If

Page 32 of 37 Revised: February 16, 2023

the missing data are extensive, model-based approaches will estimate their effects under various assumptions regarding missingness.)

Missing data will be considered based on the extent and intensity of the missingness. Steps have been implemented to reduce missingness such as researcher administered surveys, and so we anticipate that missing data will occur randomly. If missing data is extensive, approaches to mitigate the effect of the missing data will be used to generate a functional final model.

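### Section 20.5 picks out barriers to care at interim by statistical significance, with no multiplicity control and probably in a pilot sample too small for that filter

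*Combined protocol and SAP*

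**What the plan says.** Section 20.5 opens with "Interim analyses for feasibility and fidelity will be conducted aligned with the Replicating Effective Programs". It gives logging of nurse time as an example and then adds "as well as analyses to identify statistically significant barriers to accessing care after release". Significance is thus the stated criterion for naming a barrier. The section does not give the level, the candidate barriers, the outcome and its window, the number or timing of looks, or the dataset. No multiplicity rule appears anywhere in the document.

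Other sections bear on the point:

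- **Size.** Section 20.2 says "Our recruitment goal is 220 individuals" and explains that "The proposed sample size was chosen by considering what would be an appropriate case load". It gives no power, significance level or effect size.
- **Candidate factors.** Section 13.4 lists what is collected from participants, beginning with "Social Determinates of Health plan post-release" (housing, employment, transportation, health literacy). It continues through family support, incarceration history and pre-incarceration circumstances. It is a list of data elements and is not presented as a list of barriers.
- **Dataset.** Section 20.3 defines only the administrative cohort. Section 3.0 puts that at about 20,000 people.
- **Use of results.** Section 2.1 says that preliminary data from the completed pilot will serve the planning of later studies.

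**The concern.** A significance filter does three things when the sample is small and the candidates are many. It lets some chance associations through. It passes mainly those estimates of real barriers that happen to be too large. It leaves out real barriers of moderate size. The filter also fits poorly with a pilot whose main hypothesis is feasibility and acceptability.

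At stake is the list of barriers that the pilot reports and hands to the planners of the next study. That list could contain spurious entries, inflated effects and gaps.

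**Working it through.** **1. The plan's own figure.** The documents give no error rate or power for these tests. The only sample-size arithmetic is the recruitment projection in sections 4.0 and 20.2, and it reproduces:

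- Oakhill: (112 + 62) × 0.5 / 12 = 7.25, taken as 7 per month; 7 × 24 = 168.
- REECC: (65 + 64) × 0.5 / 12 = 5.375, taken as 5 per month; 5 × 24 = 120.
- Total: 168 + 120 = 288, against a goal of 220.

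This supports recruitment. It says nothing about what barrier tests could detect.

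**2. Inputs.**

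- Per-test level: two-sided 0.05 (assumed).
- Number of tests: not stated. Section 13.4 has 13 participant-reported items: housing, employment, transportation, health literacy, family support, prison years, jail years, number of incarcerations, current time served, substance history, prior primary care, prior insurance and prior homelessness. I use 5, 10 and 13.
- Visit rate: section 1.2 reports that within 30 days of release "approximately 34% of the study population has at least one outpatient visit".
- Number analysed: not stated. The goal of 220 is the ceiling. The success criteria in section 2.1 accept enrolment of "at least 50% of the targeted sample size of 220", which is 110, and "fewer than 50% of participants being lost to follow-up after" release. Half of 110 is 55. I use 55, 110 and 220.
- Factor prevalence: 50% (assumed).

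**3. Chance barriers.** With k independent tests and no real barrier, P(at least one significant) = 1 − 0.95^k.

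| k | Probability |
|---|---|
| 1 | 5% |
| 2 | 10% |
| 5 | 23% |
| 10 | 40% |
| 13 | 49% |

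If the test statistics are correlated at 0.5, simulation gives 18% for 5 tests and 29% for 10.

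**4. Missed barriers.** With m = n/2 per group, SE = √{[p1(1 − p1) + p2(1 − p2)]/m} and power ≈ Φ(|p1 − p2|/SE − 1.96). Both gaps are centred on 34%.

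For example, for 39% against 29% at n = 110: SE = √[(0.2379 + 0.2059)/55] = 0.0898; 0.10/0.0898 − 1.96 = −0.85; power is 20%.

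**5. Exaggeration.** I simulated two-proportion z-tests and divided the mean absolute significant difference by the true gap.

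| True gap | n | Power | Overstatement if significant |
|---|---|---|---|
| 10 points (39% vs 29%) | 55 | 12% | 3.1 times |
| | 110 | 20% | 2.2 times |
| | 220 | 35% | 1.7 times |
| 20 points (44% vs 24%) | 55 | 36% | 1.7 times |
| | 110 | 62% | 1.3 times |
| | 220 | 89% | 1.1 times |

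Placing the 10-point gap at 34% against 24% gives 13%, 21% and 37% power. In the related cases tried, a 30/70 split lowers power.

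**6. Would multiplicity control alone be enough?** No. Bonferroni over 10 tests uses 0.005 each and brings the chance of a false barrier to 1 − 0.995^10 = 4.9%. But power for 50% against 35% at n = 110 then falls from 35% to 11%.

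**The case against.** The strongest reply is that section 20.5 names no dataset, while section 20.3 defines only the population cohort and section 20.4 plans association analyses with factors that may influence outcomes. If the interim tests use that cohort, low power and exaggeration largely disappear and only multiplicity is left. This stands as a limit. The pilot reading is still the more natural one, because the sentence concerns feasibility and fidelity and sits beside nurse time logs, which exist only for pilot participants.

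The scenarios can also be called pessimistic. Visits may come from Medicaid data, collected for a year after release (section 12.1), or from clinic records (section 8.1), so loss to survey follow-up need not shrink the sample to 55. The 13 items overlap and may not all be tested; with one or two tests the chance of a false barrier is only 5% to 10%. All of this is fair, and it is why ranges are shown.

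Uncorrected exploratory testing is common in pilots, and significance is not the only route to a barrier here: section 13.1 plans 30 exit interviews. That lowers the stakes but does not defend the filter.

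A reader might go further and infer that the programme will be changed on chance findings, that non-significant barriers will be discarded for good, or that the same factors will be tested again at the end. The documents say none of this. Section 2.1 places the learning after completion of the pilot.

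**Conclusion.** The point holds in limited form. Section 20.5 makes significance the criterion for naming barriers and controls no error rate. If pilot participants are analysed, a moderate barrier (10 points) would usually be missed and, when found, overstated even at the full 220. A large one (20 points) would usually be found at 220 with little distortion, but less reliably at 55 or 110. Five or more tests carry roughly a one-in-five chance or higher of a spurious barrier when none is real, allowing for correlation.

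These sizes rest on the assumed level, number of tests, number analysed, factor prevalence and gap, because the plan states none of them.

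It would be wrong to infer that the trial's main conclusions are at risk. No stopping rule, primary endpoint or success criterion depends on this look, so no confirmatory error rate is inflated. The harm is confined to misleading exploratory conclusions and to the planning of later studies. The change is worth considering because it is nearly free; it is not a condition for the pilot to proceed.

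**What to change.** In section 20.5, replace the clause on identifying significant barriers with:

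> Among pilot participants released at least 30 days before the data cut, for each participant-reported social, incarceration-history and pre-incarceration factor in 13.4 (identifiers excluded), report its distribution and its association with a non-emergency outpatient visit within 30 days of release (difference in proportions for yes/no factors; odds ratio per stated unit for numeric factors) with a 95% confidence interval. These analyses are exploratory; barriers are not selected by significance, and all factors are carried to the final analysis.

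The 30-day window matches the aim in section 13.1 and the benchmark in section 1.2. If the population cohort is intended instead, the section should say so and state how multiplicity is handled. No log of programme changes is needed, because the protocol describes no adaptation driven by the interim.

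The cost is wording only: no new data, participants or procedures. The downside is that the interim yields no short list of significant barriers. The intervals will be wide: with an even split and the largest binomial variance, the half-width 1.96 × √(0.25 × 2/(n/2)) is about 26, 19 and 13 points at n = 55, 110 and 220. That width shows readers how little the interim can settle.

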# 21.0 Potential Benefits to Participants

21.1 Describe the potential benefits that individual participants may experience from taking part in the research. Include the probability, magnitude, and duration of the potential benefits.

Individual participants will receive the direct benefit of additional discharge support during the release and reentry process, including tailored health teaching and primary care services after release from prison.

21.2 Indicate if there is no direct benefit. Do not include benefits to society or others in this section.

N/A

# 22.0 Risks to Participants

22.1 List the reasonably foreseeable risks, discomforts, hazards, or inconveniences to the participants related the participants' participation in the research. Include as may be useful for the IRB's consideration, a description of the probability, magnitude, duration, and reversibility of the risks. Consider physical, psychological, social, legal, and economic risks.

We believe this study should be categorized as minimal risk since the potential risks detailed below are not believed to be greater than that is normally encountered in their daily lives, or in the routine medical, dental, or psychological examination of healthy persons. All research staff are educated and trained in the areas of confidentiality, HIPPA, and safety. There is also the extra layer of protection covered by the Certificate of Confidentiality.

There could be a breach of confidentiality that could result in disclosure of research data outside of the study team. This could carry economic or legal risks for subjects. To prevent this, all subjects will be assigned a unique identifier. These lists will be kept in a locked file in the UW Madison office and will not be shown to staff. Data collected from clinic records will have the name removed and the unique identifier will be attached by the UW study coordinator. Meetings will be conducted by staff trained in protecting participant confidentiality. Project staff who have access to the data will not have access to subject names. No clinic staff who have direct contact with the subjects will have access to data until the names are removed and the data is labeled with the blind code number.

All visits with the Nurse Case Manager will be completed in a private office. After the participant has released from prison, the Nurse Case Manager will complete all phone calls in a private setting. Participants will be encouraged to complete phone calls in a private setting.

Participant subjects might use the phone for unintended harmful purposes such as procuring drugs or alcohol.

22.2 If applicable, describe risks associated with participants delaying, being withdrawn from, or being asked to forgo standard treatment to participate in the study. Examples include holding medication prior to study visits, weaning off a standard medication, or receiving investigational treatment instead of an effective standard therapy.

Page 33 of 37 Revised: February 16, 2023

# Not applicable

22.3 If applicable, indicate which procedures may have risks to the participants that are currently unforeseeable.

# Not applicable

22.4 If applicable, indicate which procedures may have risks to an embryo or fetus should the participant be or become pregnant.

